# 9.1.2. Sample Size Re-estimation

width)

No formal sample size re-estimation is planned. The time required for the expected number of enrolled patients to have an event will depend on the rate of patient accrual and premature loss to follow-up and the median survival and progression free survival. The number of patients to be recruited may be revised if necessary to achieve the number of events necessary to perform the desired analyses.

# 9.2. Data Analysis Considerations

#### 9.2.1. Analysis Populations

All patients who receive at least one dose of study treatment will be evaluable for both effectiveness and safety and will comprise the All Treated Patients (AT) population.

The Measurable Disease (MD) population will comprise all patients who had measurable disease at baseline. This population will be the primary population for the analysis of Overall Response Rate.

#### 9.2.2. Treatment Comparisons

#### 9.2.2.1. Primary Comparisons of Interest

As this is a single arm study, there are no treatment comparisons. Effectiveness (OS and PFS), safety and health outcome endpoints will be summarized utilizing the AT population. Evaluation of overall response rates will be restricted to those patients with measurable disease at baseline (i.e., the MD population).

#### 9.2.3. Interim Analysis

Interim analyses may be conducted and will be fully described in the RAP.

# 9.2.4. Key Elements of Analysis Plan

The demographic and clinical profile of the study population will be described using baseline data. Continuous variables (e.g., age) will be reported as means, medians, ranges and standard deviations, as appropriate. Categorical variables (e.g., gender, race/ethnicity) will be summarized as number and percentage (%) of the total study population. Statistical analyses will be fully described in the written statistical analysis plan RAP. Evaluations and interpretations will be based on point estimates and 95% confidence intervals (CI) as evaluation of the statistical precision around the point estimate, where relevant. Effectiveness and safety analyses will be stratified by patient risk category, performance status (ECOG) and age (< 65 and  $\ge$  65 years) at enrollment, where relevant. Analyses may be additionally stratified by prior treatment, history of nephrectomy, histologic subtype and other characteristics as appropriate and as the distribution of characteristics allow. No formal hypothesis or statistical significance testing is planned. This approach follows the *Guidelines for Good Pharmacoepidemiology Practices*, Section D, point 10.

Data will be listed and summarized according to the GSK reporting standards, where applicable. Complete details will be documented in the RAP. Any deviations from, or additions to, the original analysis plan described in this protocol will be documented in the RAP and final study report.

As it is anticipated that accrual will be spread thinly across centers and summaries of data by center would be unlikely to be information, data from all participating centers will be pooled prior to analysis. All data up to the time of study completion/withdrawal from study will be included in the analysis, regardless of duration of treatment. There will be no imputation for missing data.

For the analysis of overall survival, the last date of known contact will be used for those patients who have not died at the time of analysis; such patients will be considered censored.

Progression will be determined by tumour response assessed by imaging or by clinical deterioration, whichever comes first, and regardless of whether treatment was discontinued or modified. For the analysis of PFS, if the patient received subsequent anticancer therapy prior to the date of documented progression or death, progression free-survival will be censored at the last adequate assessment (e.g., assessment where visit level response is complete response, partial response or stable disease) prior to the initiation of therapy. Otherwise, if the patient does not have a documented date of progression or death, progression-free survival will be censored at the date of the last adequate assessment. Further details on rules for censoring will be provided in the RAP.

Details on the determination of tumour response are given in Appendix 2. Additional details on effectiveness analyses are provided in Section 9.2.4.1. Similarly additional details on safety analyses are provided in Section 9.2.4.1.

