# 3. STUDY DESIGN

This is a global, multi-centre, long-term, prospective, observational study to evaluate treatment patterns and clinical outcomes in patients with advanced or metastatic RCC treated for the first time with pazopanib. The study is designed to enroll approximately 700-1000 patients in over the course of an enrollment period of approximately 18 months. Sites will be contacted and qualified by the estimated number of advanced or metastatic RCC patients available for enrollment annually. To the extent possible, consecutive patients meeting inclusion/exclusion criteria will be enrolled. Sites will be required to maintain a patient enrolment log of eligible patients at their treatment centres. This log will document how patients came to be included or excluded from the study, in order to assess the representativeness of the study population. The overall number of patients and sites may be adjusted during the study to meet enrollment goals, if needed. Eligible patients will be enrolled by medical oncologists and potentially by urologists experienced in the management of patients with RCC, if consistent with local practice.

There are no protocol—mandated visits or procedures associated with the study. Each patient is expected to participate for a maximum of 30 months or until premature discontinuation (i.e., due to death, withdrawal of consent, lost to follow-up or study termination). Patient completion is defined in Section 4. Follow-up information will be collected approximately every 3 months (a window of  $\pm$  4 weeks around the date of the suggested data collection will be allowed). If the patient is not seen for a regularly scheduled visit at that time, the site may contact the patient by telephone to solicit information regarding the events of interest and to limit loss to follow up. It is anticipated that frequency of patient assessment and imaging will differ according to local standard practice; therefore the quarterly data collection time points are intended to collect all assessments (with the date of assessment) since the previous visit date.

Supplementary study conduct information not mandated to be present in this protocol is provided in the accompanying Study Procedures Manual (SPM). The SPM will provide the site personnel with administrative and detailed technical information that does not impact patient safety.

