# 4. PATIENT SELECTION AND DISCONTINUATION/COMPLETION CRITERIA

#### 4.1. Patient Selection Criteria

#### 4.1.1. Number of Patients

Approximately 700-1000 patients will be enrolled. See Section 9.1.1 for sample size assumptions.

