# 7.3.4. Response Criteria

Since PRINCIPAL is not a clinical trial but an analysis of real world treatment population, no specific criteria for the evaluation of response (e.g., RECIST) is specified. Participating physicians are asked to assess tumour responses according to local processes and their own medical judgment. Because timing of assessments may be further apart than is seen in a typical RCT, any calculation of time to progression will be evaluated with appropriate caution and sensitivity analyses will be performed where feasible and relevant.

For the purposes of categorizing response in patients with measurable lesions, general guidance consistent with RECIST 1.1 is provided in Appendix 2.

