#### **Progression-Free Survival**

In VEG105192, the PFS rate at 12 months (estimated from the Kaplan-Meier estimate) was approximately 45% [Sternberg, 2010]. Taking this as a baseline proportion, the sample sizes (N) required for different levels of precision are shown in Table 3. These are calculated using the normal approximation to the binomial proportion distribution.

Table 3	Sample size estimates	for PFS (at 12 months	post-enrollment)
---------	-----------------------	-----------------------	------------------

Precision (half-width)	10%	5%	4%	3%
Estimated 95% CI	(35%, 55%)	(40%, 50%)	(41%, 49%)	(42%, 48%)
N	96	381	595	1057

A sample size of 700 patients will provide for a precision of less than 4% for PFS at 12 months.

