# **Relative Dose Intensity (RDI)**

Relative dose intensity (RDI) will be evaluated using a one sample t-test to compare the RDI against an estimate obtained from the Phase III registration study for pazopanib [VEG105192] using a minimal acceptable value (the average RDI obtained from the VEG105192 minus a margin of inferiority of 0.1).

The sample size is determined by the formula:  $N = (Z_{1-\alpha/2} + Z_{1-\beta})^2 * \sigma^2 / \delta^2$ 

Where  $\sigma$  is the estimated standard deviation for the RDI distribution and  $\delta$  is the difference to be detected. An  $\alpha$  (type I error) of 0.05 and  $\beta$  (type II error) of 0.10 is assumed (for 90% power).

If the mean RDI in this observational study is assumed to be the same as in VEG105192,  $\delta$  would be equivalent to the inferiority margin. However, the expected RDI in the real world setting should conceivably be slightly smaller than the RDI in the clinical trial setting, therefore for the purposes of sample size estimation a 0.05 decrement was used (i.e.,  $\delta$  = inferiority margin – 0.05).

A reasonable assumption for the standard deviation would be 0.25. The standard deviation calculated from VEG105192 was 0.185, and a larger standard deviation might be expected for an observational study. Table 4 gives the number of patients required to obtain the specified precision, assuming a standard deviation (SD) of 0.25 and a more conservative value of 0.4. Within the table, the precision is related to the SD by the formula: precision = Z[1 - alpha/2] \* SD/sqrt(N)

Table 4 Sample size estimates for RDI

Precision (half-width)	0.1	0.1	0.05	0.05	0.03	0.03
Estimated 95% C.I.	(0.775, 0.975)		(0.825, 0.925)		(0.845, 0.905)	
Std. Dev.	0.25	0.4	0.25	0.4	0.25	0.4
N	25	62	97	246	267	683

Based on the results from the sample size estimations, it can be seen that a total of 700 is sufficient to generate a power of 90% even in pessimistic assumptions (small margin of inferiority, large standard deviation for RDI and average RDI for real-world setting somewhat lower than in VEG105192).

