#### 9.2.4.1. Effectiveness Analyses

## 9.2.4.1.1. Primary Analysis

The primary analysis will evaluate the [population on OS and PFS based on the investigator's assessment, as defined in Section 7.3. Censoring rules will be outlined in detail in the RAP. PFS and OS duration will be summarised using Kaplan-Meier methods. Rates of PFS and OS at 12 months will be summarised. AT will be the primary population.

The overall response rate (ORR) will be based on the investigator assessment of overall response in the MD population. Patients with unknown or missing response will be treated as non-responders, i.e. they will be included in the denominator when calculating the percentage. Separate summaries of the number and percentage of patients with only non-measurable disease who achieve a best response of CR or SD will be provided. Exact methods for calculated confidence intervals will be utilized.

Several sensitivity analyses will be conducted in order to confirm the results of the primary analysis. Some key sensitivity analyses are provided below. Additional sensitivity analyses will be defined in the RAP.

- 1. The first sensitivity analysis, limited to the MD population, will be based on investigators' assessment of progression together with clinical evidence of symptomatic deterioration determined by investigator. This analysis will take into account the fact that some patients may have progression based on clinical evidence of symptomatic deterioration prior to documentation of progression via CT/MRI.
- 2. The second sensitivity analysis will be based on the patients in the MD population for whom follow-up was conducted consistent with RECIST 1.1.
- 3. The third sensitivity analysis will take into account the extended lost-to-follow up. If a progression event occurs after an extended lost-to-follow-up time the primary analysis will censor those patients at the date of their last visit with an adequate assessment even if subsequent information is available regarding tumour measurements or date of death. The extended lost-to-follow-up will be defined in the RAP.
- 4. The fourth sensitivity analysis will assign the start date of the new anti-cancer therapy as the progression date for patients who start a new anti-cancer therapy without documented disease progression in the primary analysis.

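### Precision and power in section 9.1.1 treat patients as independent although they enter through sites and are assessed locally; if outcomes correlate within site, intervals will be too narrow by an amount the protocol does not fix

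*Protocol*

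**What the plan says.** **Sampling.** Section 3 of the protocol describes a multi-centre study: "Sites will be contacted and qualified by the estimated number of advanced or metastatic RCC patients available for enrollment annually". Eligible patients are then enrolled consecutively as far as possible. Section 4.1.1 sets the size: "Approximately 700-1000 patients will be enrolled". The number of sites and the patients expected per site are not given.

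**Local determination.** Section 4.2.1 leaves pazopanib treatment to the treating physician. Section 3 expects that "frequency of patient assessment and imaging will differ according to local standard practice". Section 7.3.4 adds: "Participating physicians are asked to assess tumour responses according to local processes and their own medical judgment". Section 10.10 rules out an independent review committee.

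**Planning.** For the 12-month PFS sample sizes, section 9.1.1 states: "These are calculated using the normal approximation to the binomial proportion distribution". The ORR table uses the same method. With 700 patients the half-width for PFS is said to be under 4 percentage points. For RDI the section concludes that "a total of 700 is sufficient to generate a power of 90% even in pessimistic assumptions".

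**Analysis.** Section 9.2.4 expects few patients per centre, regards by-centre summaries as uninformative, and therefore pools: "data from all participating centers will be pooled prior to analysis". It bases interpretation on point estimates with 95% confidence intervals. Section 9.2.4.1.1 uses Kaplan-Meier methods for PFS and OS, and for ORR says: "Exact methods for calculated confidence intervals will be utilized". Section 9.2.4.3 summarises RDI by the proportion reduced and by median and range, and names no interval. Full statistical detail is left to the analysis plan (RAP), which is not at hand.

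**The concern.** Patients at one site share the people and habits that set their dose changes, scan dates and response calls. Positive within-site correlation is therefore the natural expectation for RDI, PFS and ORR. In a randomised trial much of such variation can cancel in the comparison of arms. In a single-arm study it goes straight into the variance of each estimate.

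The reason given for pooling answers a different question. Few patients per centre is a good reason not to tabulate by centre. It limits the effect of clustering on the variance but does not remove it, and a few large sites can bring it back.

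At stake is how firmly the study can claim to know its real-world estimates, including when they are set beside VEG105192. Section 9.1.1 also states its precision and power without saying that they assume independence. Point estimates are not affected.

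**Working it through.** **Inputs from the protocol.** N = 700, upper end 1000; 12-month PFS 45%; ORR 30%; RDI standard deviation (SD) 0.25 or 0.4; δ = 0.05 (margin 0.1 less the 0.05 decrement); two-sided α = 0.05; power 90%.

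**Assumptions, because the protocol gives no figures.** ICC 0.01, 0.05 and 0.10; mean patients per site m = 3, 5 and 10; coefficient of variation (CV) of site size 0 (equal sites) or 1 (very unequal).

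**1. Reproduce the plan under independence.**

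- N = 1.96² p(1−p)/h² gives 96, 381, 595 and 1057 for PFS and 81, 323, 505 and 897 for ORR, as printed.
- N = (1.96 SD/h)² gives 25, 62, 97, 246, 267 and 683 for RDI, as printed.
- PFS half-width at 700: 1.96 √(0.45 × 0.55/700) = 3.69 points. ORR, if all 700 count: 1.96 √(0.30 × 0.70/700) = 3.39 points.
- RDI, SD 0.4: N for 90% power = (1.96 + 1.2816)² × 0.4²/0.05² = 672.5, so 673. Power at 700 = Φ(0.05 √700/0.4 − 1.96) = 91.1%.

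The plan's figures are therefore correct, and they rest on independent patients.

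**2. Add clustering.** Design effect DE = 1 + ((1 + CV²)m − 1) × ICC. The half-width is multiplied by √DE. Coverage of the unadjusted interval is 2Φ(1.96/√DE) − 1. RDI power is Φ(0.05 √(700/DE)/0.4 − 1.96). Results for N = 700 and equal sites, each cell at ICC 0.01 / 0.05 / 0.10:

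| Patients per site | DE | Coverage of nominal 95% CI | PFS half-width, points | RDI power, SD 0.4 |
|---|---|---|---|---|
| 3 | 1.02 / 1.10 / 1.20 | 94.8 / 93.8 / 92.6% | 3.72 / 3.87 / 4.04 | 90.6 / 88.4 / 85.5% |
| 5 | 1.04 / 1.20 / 1.40 | 94.5 / 92.6 / 90.2% | 3.76 / 4.04 / 4.36 | 90.0 / 85.5 / 79.8% |
| 10 | 1.09 / 1.45 / 1.90 | 94.0 / 89.6 / 84.5% | 3.85 / 4.44 / 5.08 | 88.6 / 78.4 / 67.0% |

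With CV 1, DE at a mean of 5 per site is 1.09 / 1.45 / 1.90, the same as for equal sites of 10. At a mean of 10 it is 1.19 / 1.95 / 2.90, with coverage 92.8 / 84.0 / 75.0%.

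Coverage above uses the normal approximation. The exact binomial interval is slightly conservative: in simulation at p = 0.30, ICC 0.05 and equal sites it covered about 93.6% at 5 per site and 90.5% at 10, against 92.6% and 89.6% in the table.

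**3. Find where each statement stops holding.**

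- PFS under 4 points at N = 700: DE ≤ (4/3.685)² = 1.18. With equal sites this is reached at an ICC of 0.18/(m − 1): about 0.09 at 3 per site, 0.045 at 5 and 0.02 at 10.
- ORR under 4 points: DE ≤ (4/3.395)² = 1.39 if all 700 count. ORR is restricted to patients with measurable disease, so the limit is that number divided by about 504, and is tighter.
- RDI 90% power, SD 0.4, N = 700: DE ≤ 700/672.5 = 1.04. With equal sites this is an ICC of about 0.02 at 3 per site and 0.01 at 5.
- RDI, SD 0.25: N for 90% power is 672.5 × (0.25/0.4)² = 262.7, so the limit is 700/262.7 = 2.66.
- At N = 1000 the limits are 1.18 × 1000/700 = 1.68 for PFS and 1000/672.5 = 1.49 for RDI at SD 0.4.

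**The case against.** The strongest reply is that pooling does not fix a variance estimator. Kaplan-Meier methods can carry a site-clustered variance, the RDI analysis names no interval, and details are deferred to the RAP. This stands: a reader might infer from section 9.2.4 that all intervals will be computed as if patients were independent, and the protocol does not say so. Only the ORR interval is fixed by type, and an exact interval in its standard binomial form does assume independence.

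A reader might also infer that the intervals for all four endpoints are too narrow as a matter of fact. The protocol does not support that either. It gives no ICC, number of sites or site size, and the one hint, thin accrual, points to small clusters. At 3 patients per equal-sized site and ICC 0.05, coverage is 93.8% and the PFS half-width 3.87 points, so the PFS statement stands. OS is less exposed, since death is not a local judgement, though case mix and care can still cluster.

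The power loss is also sensitive to the SD. The protocol calls 0.25 reasonable and 0.4 more conservative; at 0.25, power at N = 700 is still 99.3% with DE 1.45. At N = 1000, SD 0.4 and DE 1.45 it is 90.7%.

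Related safeguards exist: section 9.2.4.1.2 examines consistency of assessment timing across sites, and section 9.2.4.1.1 has a RECIST-consistent sensitivity analysis. Neither corrects a variance.

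What the reply does not rescue is the reason for pooling, read as a reason to ignore site in the variance, or the unqualified statements in section 9.1.1. The RDI statement claims to cover pessimistic assumptions and has only about 4% to spare on the design effect.

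**Conclusion.** The point holds conditionally, as an inexpensive improvement rather than an error in the plan's arithmetic, which reproduces. If outcomes correlate within site, intervals that ignore site will be too narrow for ORR, PFS and RDI, and less so for OS. The size depends on quantities the protocol does not give. For N = 700, equal sites and an assumed ICC of 0.01 to 0.10, nominal 95% coverage runs from 94.8% to 92.6% at 3 patients per site, 94.5% to 90.2% at 5 and 94.0% to 84.5% at 10, and is lower with very unequal sites. The PFS precision statement survives up to a design effect of about 1.18. The RDI power statement at SD 0.4 survives only up to about 1.04. At SD 0.25, or with enrolment near 1000, there is ample room in most scenarios.

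**What to change.** **Section 9.2.4.** Keep the pooled point estimates. Add that 95% confidence intervals for 12-month PFS and OS, ORR and mean RDI will also be given with variance clustered on site (sandwich estimator or site bootstrap), with the clustered ORR interval shown beside the exact one. Report the number of sites, the distribution of site sizes and the estimated ICC for each endpoint.

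**Section 9.1.1.** State that the precision and power figures assume independent patients, and give the design effect at which each stops holding: at N = 700, about 1.18 for PFS, 1.39 for ORR if all 700 have measurable disease, and 1.04 for RDI at SD 0.4 (2.66 at SD 0.25). Do not write a single assumed ICC, or a power figure derived from one, into the protocol.

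**Cost.** Slightly more analysis work and somewhat wider intervals. No new patients or data are needed, because sites enter the data themselves and can be identified. If accrual is as thin as expected or the ICC is near zero, the clustered intervals will hardly differ from the planned ones.

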#### 9.2.4.1. Effectiveness Analyses

## 9.2.4.1.1. Primary Analysis

The primary analysis will evaluate the [population on OS and PFS based on the investigator's assessment, as defined in Section 7.3. Censoring rules will be outlined in detail in the RAP. PFS and OS duration will be summarised using Kaplan-Meier methods. Rates of PFS and OS at 12 months will be summarised. AT will be the primary population.

The overall response rate (ORR) will be based on the investigator assessment of overall response in the MD population. Patients with unknown or missing response will be treated as non-responders, i.e. they will be included in the denominator when calculating the percentage. Separate summaries of the number and percentage of patients with only non-measurable disease who achieve a best response of CR or SD will be provided. Exact methods for calculated confidence intervals will be utilized.

Several sensitivity analyses will be conducted in order to confirm the results of the primary analysis. Some key sensitivity analyses are provided below. Additional sensitivity analyses will be defined in the RAP.

- 1. The first sensitivity analysis, limited to the MD population, will be based on investigators' assessment of progression together with clinical evidence of symptomatic deterioration determined by investigator. This analysis will take into account the fact that some patients may have progression based on clinical evidence of symptomatic deterioration prior to documentation of progression via CT/MRI.
- 2. The second sensitivity analysis will be based on the patients in the MD population for whom follow-up was conducted consistent with RECIST 1.1.
- 3. The third sensitivity analysis will take into account the extended lost-to-follow up. If a progression event occurs after an extended lost-to-follow-up time the primary analysis will censor those patients at the date of their last visit with an adequate assessment even if subsequent information is available regarding tumour measurements or date of death. The extended lost-to-follow-up will be defined in the RAP.
- 4. The fourth sensitivity analysis will assign the start date of the new anti-cancer therapy as the progression date for patients who start a new anti-cancer therapy without documented disease progression in the primary analysis.
- 5. The fifth sensitivity analysis will utilize alternative methods for handling patients with unknown or missing response in evaluation of ORR (methods will be defined in the RAP).

